4.9.2. Additional Secondary Efficacy Analysis

Other secondary efficacy measures will be summarized by treatment and nominal visit. Unless otherwise specified, missing data will not be imputed and assessments are not subject to type 1 error rate control. The analyses will be conducted based on the efficacy estimand.

4.9.2.1. Analysis of 7-point SMBG Profile

The 7-point SMBG profiles consist of pre-meal and 2-hour postprandial SMBG measurements for the morning, midday, and evening meals, and one measurement at bedtime. Patients will be asked to perform two 7-point SMBG profiles over a 24-hour period on 2 nonconsecutive days, in the 2-week period prior to prespecified office visits (Visits 3 [Week 0], 9 [Week 24], and 11 [Week 40]). In general, the mean of the two daily values will be used for reporting purpose. If more than 2 SMBG profiles are available, the 2 most recent profiles on nonconsecutive days should be used.

The following variables for 7-point SMBG profile will be analyzed using MMRM model:

1. Pre morning meal BG
2. 2-hour postprandial measurement for morning meal BG
3. Pre midday meal BG
4. 2-hour postprandial measurement for midday meal BG
5. Pre evening meal BG
6. 2-hour postprandial measurement for evening meals BG
7. Bedtime BG
8. Morning pre-meal to 2-hour postprandial BG excursion
9. Midday pre-meal to 2-hour postprandial BG excursion
10. Evening pre-meal to 2-hour postprandial BG excursion
11. Mean of all pre-meal BG
12. Mean of all 2-hour postprandial BG
13. Mean of all meals 2-hour excursion
14. Mean of all 7-point BG

For before and 2 hours after meal BG and bedtime BG (Reports 1-7), the mean BG value at each visit is calculated as the average of 2 daily BG values. The glucose excursion for morning, midday and evening meals is calculated as the difference between 2-hour postprandial measurements and pre-meal measurements.

For mean of all pre-meal BG (Report 11), the pre-meal daily mean is calculated as the average BG values collected for before morning, midday and evening meals on a particular day. The mean of all pre-meal BG at each visit is calculated as the average of 2 pre-meal daily means.

For mean of all postprandial BG (Report 12), the post-meal daily mean is calculated as the average of 2-hour postprandial BG values of morning, midday and evening meals on a particular day. The mean of all postprandial meals BG at each visit is calculated as the average of 2 post-meal daily means.

For mean of all meals 2-hour excursion at each visit (Report 13), the daily mean for all meals is calculated as the average of glucose excursion for morning, midday and evening meals on a

particular day. The mean of all meals 2-hour excursion at each visit is calculated as the average of 2 daily means.

For mean of all 7-point BG (Report 14), the daily mean is calculated as the average of 7 BG values collected on a particular day. The mean of all 7-point BG at each visit is calculated as the average of 2 daily means.

Actual and change from baseline of 7-point SMBG will be summarized using mITT population, and analyzed using MMRM with treatment, any past prior use (yes or no) of any antihyperglycemic medication, visit, baseline HbA1c strata ($<8.5\%$, and $\geq 8.5\%$) and treatment-by-visit interaction, baseline 7-point SMBG, baseline 7-point SMBG-by-visit interaction as covariates. An unstructured covariance structure will be used to model the within-patient variability and implicitly adjusts for missing data. If this analysis fails to converge, then other covariance structures will be tested in the order mentioned in Section 4.8.3.

4.9.2.2. Proportion of Participants with Weight Loss of $\geq 5.0\%$, $\geq 10\%$ and $\geq 15\%$ at Week 40

The analysis for the proportion of participants with target weight loss at Week 40 will be conducted in a manner similar to Section 4.9.1.1 based on the efficacy estimand. Baseline HbA1c category ($\leq 8.5\%$, $> 8.5\%$ [≤ 69 , > 69 mmol/mol]) will be used as a fixed factor in place of baseline HbA1c as a covariate and baseline of the corresponding variable will be used as an additional covariate in the statistical model.

A large rectangular area of the page is completely redacted with a solid red color, obscuring several lines of text that would normally be present in that section.

4.11. Safety Analyses

Unless specified otherwise, safety assessments will be based on the SS (see Section 3). All events that occur between the date of first dose of study drug to the date of patient's safety follow-up visit or patient's end of study participation will be included. Selected safety analyses may be conducted after excluding data after the introduction of another antihyperglycemic therapy. For rare events (<10 patients have the events), summary tables may not be generated, and individual patient level data will be listed.

Unless specified otherwise, comparisons of tirzepatide doses to placebo will be performed. For selected continuous safety parameters, difference among treatment mean change from baseline at scheduled visits will be assessed via a MMRM using REML. The model will include baseline HbA1c ($\leq 8.5\%$, $> 8.5\%$ [≤ 69 , > 69 mmol/mol]), any past prior use (yes or no) of any antihyperglycemic medication, treatment group, visit, treatment-by-visit interaction, baseline

value of the safety parameter and baseline of the safety parameter-by-visit interaction. To model the covariance structure within patients, the unstructured covariance matrix will be used. If this model fails to converge, the covariance structures specified in Section 4.8.3 will be tested in order.

For selected safety parameters, time-to-first-event analysis via cox-proportional hazards model may be conducted. For patients experiencing an event, “time-to-first-event” will be the time to the first occurrence of the event. For patients without the event, “time-to-event” will be censored at end of study participation (study discontinuation, safety follow-up visit, or date of death).

Where specified, rate of events will be analyzed using a generalized linear mixed-effects model assuming the number of events follow a negative binomial distribution, and with treatment as a fixed effect. The logarithm of years in specified time interval will be adjusted as an offset to account for possible unequal treatment duration in specified time interval between patients.

For safety interpretation, p-values will not be used for hypothesis testing. P-values will be considered as a number between 0 and 1 that gives an idea of how strong the evidence is for an imbalance between study intervention arms. The evidence for an imbalance is stronger toward 0 and weaker toward 1. Similarly, confidence intervals will not be used for hypothesis testing. They reflect the uncertainty of an estimate.

The definition of baseline and postbaseline are provided in [Table GPIU.4.1](#).

Table GPIU.4.1. Baseline and Postbaseline Definition for Safety Analysis

Analysis Set	Analysis Type	Baseline	Postbaseline
SS	1.1) Treatment-Emergent Adverse Events	The baseline period is defined as the start of screening and ends prior to the first dose of study treatment (typically at Week 0). If the first dose date is missing then the randomization date will be used instead of first dose date.	Starts at or after the first dose of study treatment and ends at the end of the study period (including off-drug follow up visit).
SS	1.2) Treatment-Emergent Abnormal Labs and Vital Signs.	For labs, baseline period is defined as prior to the first dose time and will include all scheduled and unscheduled measurements. If the first dose time is missing then any data collected on the date of the first dose will be treated as baseline. For vital signs, baseline period is defined as measurements collected prior to the first dose. If the first dose date is missing then the randomization date will be used instead of first dose date.	Postbaseline will be defined as after the baseline period through the end of the study participation. All scheduled and unscheduled measurements will be included.
SS	1.3) Change from Baseline for Labs, and Vital Signs.	The last scheduled and unscheduled non-missing assessment recorded during the baseline period defined above (1.2).	Postbaseline will be defined as above (1.2). Only scheduled visits will be included.

Abbreviations: ED = early discontinuation; SS = Safety Analysis Set.

4.11.1. Extent of Exposure and Treatment Compliance

For the summary of duration on study treatment and study, the frequency and percentage of participants falling into the following categorical ranges will also be summarized by planned treatment group as well: >0 week, ≥ 4 weeks, ≥ 8 weeks, ≥ 12 weeks, ≥ 16 weeks, ≥ 20 weeks, ≥ 24 weeks, ≥ 38 weeks.

Treatment compliance is defined as taking at least 75% of required injections of study intervention. Compliance will be calculated by taking the number of doses administered (regardless of the actual dose administered) divided by the total number of doses expected to be administered $\times 100$. Frequency, counts and percentages of participants compliant to study intervention will be summarized by treatment arm using the mITT population. Overall study drug compliance will be evaluated for participants administered >4 planned doses.

A listing of patients who re-initiate due to missing ≥ 3 consecutive doses may be produced.

4.11.2. Adverse Events

For adverse events (AEs), the most recent Medical Dictionary for Regulatory Activities (MedDRA) version that accommodates the data lock timeline is to be applied. Adverse events will be coded from the actual term using the MedDRA and reported with preferred terms and system organ class. Selected notable AEs of interest may be reported using high-level terms or Standardized MedDRA Queries.

Treatment-emergent adverse events

A treatment-emergent adverse event (TEAE) is defined as an event that first occurred or worsened in severity after the first dose. The MedDRA Lowest Level Term (LLT) will be used in the treatment-emergent derivation. The maximum severity for each LLT during the baseline period including ongoing medical history will be used as baseline severity. For events with a missing severity during the baseline period, it will be treated as 'mild' in severity for determining treatment-emergence. Events with a missing severity during the postbaseline period will be treated as 'severe' and treatment-emergence will be determined by comparing to baseline severity. Statistical comparisons will be applied at both the SOC and PT levels. Events will be ordered by decreasing frequency within SOC, with the SOC in alphabetical order. For events that are sex-specific, the denominator and computation of the percentage will include only patients from the given sex. The planned summaries for AEs are provided in [Table GPIU.4.2](#).

Table GPIU.4.2. Tables and Figures Related to Adverse Events

Analysis	Details	Sample
Overview of AEs	
Number and percentage of participants who reported
 
 • death • SAE • permanent discontinuation from study intervention due to an AE • permanent discontinuation from study due to an AE, and • TEAE. 	Controlled

Analysis	Details	Sample
TEAEs by PT within SOC	
Number and percentage of participants with TEAEs using MedDRA PT nested within SOC.
 
For controlled analysis sets, events will be ordered by decreasing frequency (total column) within SOC.
 
SOCs will be ordered by alphabetical order.
	Controlled
Maximum Severity TEAEs by PT	
The number and percentage of participants with TEAEs by maximum severity using MedDRA PT.
 
For each participant and TEAE, the maximum severity for the MedDRA PT is the maximum postbaseline severity observed from all associated LLTs mapping to the MedDRA PT.
 
The maximum severity will be determined based on the non-missing severities. If all severities are missing for the defined postbaseline period of interest, it will show as missing in the table.
 
Events will be ordered by decreasing frequency (total column) within SOC.
 
SOCs will be ordered by alphabetical order.
	Controlled
TEAEs Occurring at $\geq 5\%$ by PT	
Presented as a figure using study size adjusted percentages and risk differences (95% confidence intervals).
 
The number and percentage of participants with TEAEs using MedDRA PT for the TEAEs occurring in $\geq 5\%$ before rounding in any column in the table.
 
The cut off is determined based on the percentage not adjusted for study size.
 
Events will be ordered by decreasing frequency (total column) within SOC.
 
SOCs will be ordered by alphabetical order.
	Controlled
SAEs by PT within SOC	
The number and percentage of participants who reported a SAE (including deaths and SAEs temporally associated or preceding deaths) during the treatment period using MedDRA PT nested within SOC.
 
Events will be ordered by decreasing frequency (total column) within SOC.
 
SOCs will be ordered by alphabetical order.
	Controlled

Analysis	Details	Sample
Primary AE leading to permanent discontinuation of study intervention by PT within SOC	
The number and percentage of participants who permanently discontinued from study intervention due to an AE (including AEs that led to death) during the treatment period using MedDRA PT nested within SOC. Time-to-event analyses will be conducted by treatment on time to study drug discontinuation.
 
Primary AE listed on the disposition form will be used.
 
Events will be ordered by decreasing frequency (total column) within SOC.
 
SOCs will be ordered by alphabetical order.
	Controlled
Primary AE leading to permanent discontinuation of study by PT within SOC	
The number and percentage of patients who prematurely discontinue the study due to an AE will be summarized by treatment using MedDRA PT nested within SOC. Events will be ordered by decreasing frequency (total column) within SOC.
 
SOCs will be ordered by alphabetical order.
	
Listing of SAEs	
A listing of all SAEs will be provided. Listing will include and not limit to treatment, patient identification including the site number, treatment group, date of event, age at the time of enrollment, gender, MedDRA SOC and PT, whether it is TEAE, severity, action taken, outcome, relationship to study drug, time from first dose of study drug to the event, and event duration.
 
A listing of all deaths will be provided. Listing will include patient identification including the treatment, site number, date of death, age at the time of enrollment, gender, MedDRA PT of associated AE, time from first dose of study drug to death, time from last dose of study drug to death (if patient had discontinued study drug), cause of death as reported by investigator, caused of death as adjudicated by Clinical Endpoint Committee (CEC).
	mITT Population

Abbreviations: AE = adverse event; HLT = High Level Term; LLT = Lowest Level Term; LY = Lilly product number; MedDRA = Medical Dictionary for Drug Regulatory Activities; PT = Preferred Term; SAE = serious adverse event; SOC = System Organ Class; TEAE = treatment-emergent adverse event.

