10.4.2.2. Male

The table below describes contraception guidance for all men.

| Topic | Guidance |
|---|--|
| For all men | should refrain from sperm donation for the duration of the study and for 5 half-lives of study intervention, plus 90 days, corresponding 120 days (4 months) after the last dose of the study intervention. |
| Contraception for men with partners of childbearing potential | 
 • either remain abstinent (if this is their preferred and usual lifestyle), or • must use condoms during intercourse for the duration of the study, and • for 120 days (4 months) after the last dose of the study intervention. |
| Contraception for men in exclusively same sex relationships, as their preferred and usual lifestyle | Are not required to use contraception |

Examples of highly effective, effective and unacceptable methods of contraception can be found in Section [10.4.2.1](#).

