2.1. Multiplicity Adjustment

The primary and the key secondary objectives will be evaluated align to both the treatment-regimen estimand and the efficacy estimand. No multiplicity adjustment will be made for conducting analysis aligned to the two estimands.

For analysis within each estimand, $H_{5,1}$, $H_{10,1}$, and $H_{15,1}$ will be initially tested each at 0.01667 significance level. A graphical testing scheme (Bretz et al. 2009, 2011) presented in [Figure GPIU.2.1](#) will be used to strongly control for type 1 error.

[figure not shown]

Figure GPIU.2.1. Type 1 error control strategy for primary and key secondary.

3. Analysis Sets

For the purposes of analysis, the following analysis sets are defined:

Population/Analysis Set	Population/Analysis Set
Screened population	All participants who signed informed consent
Randomized population	All participants who are randomly assigned to a treatment group.
Modified intention-to-treat (mITT) population	All randomly assigned participants who are exposed to at least 1 dose of study intervention.
Efficacy analysis set (EAS): This analysis set will be used to estimate the efficacy estimand for all efficacy objectives	Data obtained during Study Period II from the mITT population, excluding data after initiating rescue antihyperglycemic medication or stopping study intervention.
Full analysis set (FAS): This analysis set will be used to estimate the treatment-regimen estimand for the primary and key secondary objectives	Data obtained during Study Period II from the mITT population, regardless of adherence to study intervention or initiation of rescue antihyperglycemic medication.
Safety analysis set (SS): This analysis set will be used to assess the safety of study treatment	Data obtained during Study Periods II or III from the mITT population, regardless of adherence to study intervention or initiation of rescue antihyperglycemic medication.

4. Statistical Analyses

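### The SAP's table of serious adverse events by preferred term stops at the end of the treatment period, a narrower window than the safety analysis set, with no reason given

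*SAP*

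**What the plan says.** The row for SAEs by preferred term (PT) within system organ class (SOC) in SAP Table GPIU.4.2 counts participants with an SAE, deaths included. Its time limit is in the words "SAEs temporally associated or preceding deaths) during the treatment period using MedDRA PT nested within SOC". SAP Section 1.2 divides the study into screening and lead-in (Period I), treatment (Period II) and safety follow-up (Period III). Visit 801 falls about 4 weeks after the last treatment visit.

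The rest of the plan uses a wider window for safety:

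- SAP Section 3 and Protocol Section 9.2 define the safety analysis set as "Data obtained during Study Periods II or III from the mITT population, regardless of adherence to study intervention or initiation of rescue antihyperglycemic medication".
- SAP Section 4.11 opens with "Unless specified otherwise, safety assessments will be based on the SS (see Section 3"). The next sentence brings in "All events that occur between the date of first dose of study drug to the date of patient's safety follow-up visit" or the end of participation.
- For treatment-emergent events, the postbaseline window in SAP Table GPIU.4.1 "ends at the end of the study period (including off-drug follow up visit").
- Protocol Section 9.3.6 bases safety assessments on the safety analysis set and names SAEs and deaths among the summaries.
- Protocol Section 8.3.1 collects SAEs up to the safety follow-up visit or the end of participation.

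**The concern.** The SAE row departs from the window that both documents set for safety data, and nothing explains why. A programmer who follows the row as written will leave out Period III events. This is the only general table that shows, by arm, which kinds of serious event occurred. Some special-interest summaries pick out severe or serious events, but each covers only its own topic.

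An SAE or death in follow-up could therefore add to the SAE count in the overview and yet have no entry in the breakdown by type. Two tables in the same report would then disagree on the number of participants with an SAE, and the reader would not be told why. With 50 participants per arm, one such participant is 1/50 = 2 percentage points in that arm.

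**Working it through.** The documents give no figure that depends on this window, so there is nothing to reproduce. The check compares the places where an SAE in follow-up would or would not appear, and then sizes the gap.

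**1. Where a Period III SAE would appear**

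| Output | Window | Period III SAE included? |
|---|---|---|
| Overview of AEs (Table GPIU.4.2): by-arm counts of deaths and SAEs | No limit in the row; safety analysis set by default | Yes |
| TEAEs by PT within SOC | Table GPIU.4.1, through off-drug follow-up | Yes if treatment-emergent, but not marked as serious |
| SAEs by PT within SOC | Treatment period | No, read literally |
| Listings of SAEs and deaths | No limit | Yes, with treatment group |
| Narratives (SAP Section 4.11.3) | To end of participation | Yes |

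Only the third output has the narrower window.

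**2. Share of the observation window**

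Inputs: 40 weeks of treatment (Protocol Section 4.2) and about 4 weeks of follow-up (SAP Section 1.2). For a completer, the share is 4 / (40 + 4) = 9.1%.

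**3. How many participants this could involve**

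This step is an illustration. The documents give no SAE rate, so I assume a risk r of 2%, 5% or 10% over 44 weeks, a constant hazard, and 200 participants (50 per arm) all followed to Visit 801.

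- Weekly hazard: h = −ln(1 − r) / 44.
- Chance of an SAE in the 4 follow-up weeks: p = 1 − exp(−4h).
- Expected number: 50p per arm and 200p in the trial.
- Chance of at least one in the trial: 1 − (1 − p)^200.

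| r | p | Per arm of 50 | Of 200 | Chance of at least one |
|---|---|---|---|---|
| 2% | 0.0018 | 0.09 | 0.37 | 31% |
| 5% | 0.0047 | 0.23 | 0.93 | 61% |
| 10% | 0.0095 | 0.48 | 1.91 | 85% |

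The participant totals in the overview and the SAE table differ only when someone's sole SAE falls in follow-up. That chance is (1 − r)^(40/44) × p, which gives 0.36, 0.89 and 1.73 expected participants of 200. A participant with SAEs in both periods is counted in both totals but could still lack a PT entry for the later event.

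**The case against.** The strongest reply is that no SAE is lost. The overview counts SAEs and deaths by arm without a period limit. Treatment-emergent follow-up SAEs also enter the TEAE table by PT and SOC, with statistical comparisons at both levels. Listings and narratives cover the rest. All of this stands, and it limits the point to one table.

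Second, the wording may simply be loose. In SAP Section 4.11 the exception clause qualifies the choice of analysis set. The sentence that brings in all events through follow-up carries no exception, so it could be held to govern the row. The row on AEs leading to discontinuation of study intervention uses the same treatment-period phrase, which suggests template text. It matters little there, because no study drug is given in follow-up. This may explain how the phrase arose, but the SAE row still states a narrower window, and a programmer should not have to guess which sentence prevails.

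Third, SAP Section 4.11 allows summary tables to be dropped for events in fewer than 10 patients. At a 2% risk, 0.02 × 200 = 4 participants would have an SAE and the table might not be produced. That is fair, but the row should be right if the table is produced.

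A reader might also lean on drug exposure. Protocol Section 10.4.2.2 tells men to refrain "for 5 half-lives of study intervention, plus 90 days, corresponding 120 days (4 months") after the last dose, which implies 120 − 90 = 30 days for 5 half-lives, against about 28 days of follow-up. So the follow-up is not free of drug, but exposure is falling towards (1/2)^5, about 3%. The inconsistency does not depend on this argument.

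**Conclusion.** The point holds as an inconsistency in one table. Read literally, the SAE row leaves Period III SAEs and deaths out of the only general by-arm breakdown of serious events by type. This conflicts with the safety analysis set, SAP Section 4.11, Table GPIU.4.1 and Protocol Section 9.3.6, and the overview and PT/SOC totals may not agree as a result.

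Two stronger conclusions are tempting, and the documents do not support them:

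- A reader might infer that follow-up SAEs are left out of the arm comparison altogether, or are only listed. The overview counts them by arm, and the TEAE table includes the treatment-emergent ones.
- A reader might turn the 9% share of time into a claim that about 1 in 11 SAEs goes untabulated. That needs a constant SAE hazard, which the documents do not give. Protocol Section 2.3.1 says most of the commonest (gastrointestinal) events tended to occur during dose escalation. This is not specific to SAEs, but it gives no support to a flat hazard.

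The effect is probably small: about 0.4 to 1.9 participants of 200 under the assumed 2% to 10% risks. The efficacy conclusions are not affected.

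**What to change.** In the row for SAEs by PT within SOC of SAP Table GPIU.4.2, replace the words that restrict it to the treatment period with *during Study Periods II and III*. The row then matches the safety analysis set, and the change removes any doubt about participants who stop study drug early but stay in the study. If the sponsor does intend the restriction, the SAP should define it, give the reason, and add a by-arm table of SAEs in follow-up.

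The cost is one phrase in the SAP. No new data are needed, because SAEs are already collected through the follow-up visit. No protocol amendment is needed either, because the change restores the protocol's own safety analysis set.

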5.4. Screen Failures

A screen failure occurs when a participant who consents to participate in the clinical study is not subsequently assigned to study intervention. A minimal set of screen failure information is required to ensure transparent reporting of screen failure participants to meet the Consolidated Standards of Reporting Trials (CONSORT) publishing requirements and to respond to queries from regulatory authorities. Minimal information includes demography, screen failure details, eligibility criteria, and any SAE.

Individuals who do not meet the criteria for participation in this study (screen failure) must not be rescreened.

5.5. Criteria for Temporarily Delaying Enrollment/Randomization/Administration of Study Intervention of a Participant

Not applicable.

6. Study Intervention(s) and Concomitant Therapy

Study intervention is defined as any investigational intervention(s), marketed product(s), placebo, or medical device(s) intended to be administered to/used by a study participant according to the study protocol.

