6.6. Dose Modification

6.6.1. Tirzepatide

Please refer to Section 6.1.1 for tirzepatide administration. Study intervention dose modification is not permitted except for management of intolerable gastrointestinal symptoms.

Management of Participants with Gastrointestinal Symptoms

In participants who experience intolerable gastrointestinal symptoms (for example, nausea, vomiting, or diarrhea) at any time during the study, the following measures are recommended:

1. counseling on dietary behaviors that may help mitigate nausea and vomiting, (for example, eating smaller meals, splitting 3 daily meals into 4 or more smaller ones, and stopping eating when they feel full).
2. if symptoms persist despite #1, prescribing symptomatic medication (for example, antiemetic or antidiarrheal medication), at the investigator's discretion.
3. if symptoms persist despite #1 and #2, temporarily interrupting study intervention (omit 1 dose, the participant will take 3 of 4 doses at that dose level). Study intervention should be resumed at the assigned dose immediately, either alone or in combination with symptomatic medication, which can also be utilized to manage symptoms.

If intolerable gastrointestinal symptoms (for example, nausea, vomiting, or diarrhea) persist despite the above measures before or at Visit 5 (the scheduled visit in Week 8), the participant should discontinue the study intervention.

If intolerable gastrointestinal symptoms (for example, nausea, vomiting, or diarrhea) persist despite the above measures after Visit 5 (the scheduled visit in Week 8) the investigator should contact Lilly to consider continuing treatment at a lower maintenance dose of study intervention in a blinded fashion, for example:

- Participants at 5 mg will decrease the dose to placebo.
- Participants at 7.5 mg or 10 mg will decrease the dose to 5 mg.
- Participants at 12.5 mg or 15 mg will decrease the dose to 10mg.

If de-escalation of the tirzepatide dose is necessary, the investigator will use the IWRS to receive the appropriate tirzepatide dispensing information. If de-escalation is needed between scheduled visits, the IWRS will have unscheduled visits dedicated to providing dispensing information for

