participants whose dose has been de-escalated. Those participants who have their dose de-escalated, will not be escalated again. The dose can be de-escalated only once and should before Week 24 (after Week 24, dose decreases will not be allowed). After that, the participants will have to discontinue study intervention if intolerable gastrointestinal AE persists and stay in the study.

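### The AE-discontinuation table misses 5 mg participants moved to placebo for GI intolerance: they have stopped tirzepatide but still count as on study intervention

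*SAP*

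**What the plan says.** Stopping study intervention early because of adverse events is a named safety endpoint for each dose against placebo (Protocol 3, SAP 1.1). The output for it is a row of SAP Table GPIU.4.2: "The number and percentage of participants who permanently discontinued from study intervention due to an AE". The responsible event comes from the disposition form.

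The opening of Protocol Section 6 fixes the key term: "Study intervention is defined as any investigational intervention(s), marketed product(s), placebo, or medical device(s" and so on. Placebo is therefore study intervention.

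Protocol 6.6.1 sets out what happens when GI symptoms are intolerable:

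- Dietary counselling comes first, then symptomatic medication, then "temporarily interrupting study intervention (omit 1 dose, the participant will take 3 of 4 doses at that dose level".
- If symptoms "persist despite the above measures before or at Visit 5 (the scheduled visit in Week 8), the participant should discontinue the study intervention".
- After Visit 5 the investigator contacts the sponsor to "consider continuing treatment at a lower maintenance dose of study intervention in a blinded fashion". The listed step at 5 mg is "Participants at 5 mg will decrease the dose to placebo". From 7.5 or 10 mg the step is to 5 mg, and from 12.5 or 15 mg it is to 10 mg.
- "The dose can be de-escalated only once and should before Week 24", and a reduced dose is not raised again. Beyond that point, "participants will have to discontinue study intervention if intolerable gastrointestinal AE persists and stay in the study".

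SAP 4.11.4.13, extended in version 2, adds one output on this subject: GI treatment-emergent events split by whether the participant was de-escalated.

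**The concern.** At 5 mg, de-escalation is not a dose reduction in substance. It ends active treatment because of an adverse event, and it cannot be reversed. The protocol nevertheless treats it as continued study intervention, so it falls outside the endpoint that readers will use to judge how often an adverse event ended tirzepatide treatment.

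What is at stake is complete tolerability reporting for the 5 mg arm. The omission can only lower the 5 mg figure. No efficacy claim or error rate is involved, because the SAP treats safety p-values as descriptive (SAP 4.11).

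**Working it through.** The documents give no figure for de-escalation, so there is none to reproduce. The check is mainly textual.

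**1. The same event at 5 mg, by time.**

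| Intolerable GI symptoms persist | Protocol 6.6.1 | On tirzepatide afterwards? | In the AE-discontinuation row? |
|---|---|---|---|
| Up to and including Visit 5 (Week 8) | Stop study intervention | No | Yes |
| After Visit 5, before Week 24, if de-escalated | Blinded switch to placebo | No | No, unless an AE later stops the injections |
| After Week 24 | Stop study intervention | No | Yes |

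The consequence for active treatment is the same in all three rows. Only the middle one goes uncounted.

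**2. The same window at higher doses.** A participant at 7.5 or 10 mg goes to 5 mg, and one at 12.5 or 15 mg goes to 10 mg. Both stay on tirzepatide, so leaving them out of a discontinuation count is right.

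**3. Who is at 5 mg after Week 8.** Under Protocol 4.1 the 5 mg arm is at 5 mg from Week 4 onward, while the 10 and 15 mg arms move to 7.5 mg at Week 8. The route is therefore essentially confined to the 5 mg arm. The exception is a participant restarted at 5 mg after three or more consecutive missed doses (Protocol 7.1.2).

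**4. Why the disposition form would not catch it.** The switch is blinded and dispensed through the IWRS. An investigator who sees injections continue has no reason to record a discontinuation. This is an inference from the procedures; neither document says it outright.

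**5. Whether another output shows it.**

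- Compliance (SAP 4.11.1) counts injections whatever their strength, so placebo injections after the switch count as taken.
- The Kaplan-Meier analysis of stopping study intervention (SAP 4.3) rests on the same definition.
- Narratives (SAP 4.11.3) are triggered by AE discontinuation, serious events or severe events of special interest. A moderate, non-serious GI event that led to a switch triggers none of these.
- Adverse-event tables show that the GI event occurred, but not that it ended active treatment. Action taken is specified only for the listing of serious events.

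**6. Size.** With about 50 participants per arm (Protocol 1.1), one uncounted participant is 100/50 = 2.0 percentage points, and k participants are 2.0 × k points.

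For illustration only, assume 2 counted AE discontinuations in the 5 mg arm and 1 of 50 on placebo:

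| Uncounted switches k | (2 + k)/50 | Fisher p v 1/50 (descriptive) |
|---|---|---|
| 0 | 4% | 1.00 |
| 1 | 6% | 0.62 |
| 2 | 8% | 0.36 |
| 3 | 10% | 0.20 |
| 5 | 14% | 0.06 |

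If the true switch rate at 5 mg were q, the chance of at least one uncounted case would be 1 − (1 − q)^50. That gives 63.6% at q = 2%, 87.0% at 4%, 95.5% at 6% and 99.5% at 10%. These values of q are assumptions, and q = 0 is also possible.

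**The case against.** The table reports exactly the endpoint it names, and it contains no error of definition or arithmetic. De-escalation is optional, requires sponsor contact, and its steps are given as examples. In the 5 mg arm the last dose step is at Week 4, so the route applies only to symptoms that become or remain intolerable more than four weeks later. The number may well be zero. The GI events themselves appear in the planned adverse-event and maximum-severity tables, and anyone who later stops injections because of an AE is counted. All of this stands, and it limits the size of the point. It does not answer the 5 mg-to-placebo case.

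Three stronger readings are tempting, and the documents do not support them.

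- A reader might infer that every de-escalation at 10 and 15 mg is a hidden discontinuation. It is not, because those participants remain on tirzepatide. Failure to tolerate the assigned dose is a different quantity from discontinuation.
- A reader might infer that the de-escalation summary in SAP 4.11.4.13 is pooled over arms, since its sentence does not mention treatment. SAP 4.1 has data summarized by randomized assignment, SAP 4.11 makes comparison with placebo the default, and the neighbouring sentences are by treatment. By arm is the more natural reading, so only a clarification is needed.
- A reader might infer a particular size, or a bias that varies across the three doses. Risk, uptake and timing of de-escalation are not in the documents, so neither can be derived.

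**Conclusion.** The point holds for 5 mg-to-placebo switches and no further. With the plan followed as written, an AE-driven and irreversible stop of tirzepatide can be missing from the named safety endpoint. The 5 mg figure is then too low, as a measure of AE-driven cessation of active drug, by 2.0 percentage points for each such participant. The conclusion rests on three things: the Section 6 definition of study intervention, about 50 participants per arm, and the listed 5 mg step being the one used. The count is unknown and may be zero. This is a cheap improvement in reporting, not a fault in the endpoint or in the clinical rule.

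**What to change.** Leave the endpoint, the existing table row and the de-escalation rule as they are, and make three additions to the SAP:

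1. In Table GPIU.4.2, add a supplementary row by randomized arm: AE discontinuation of study intervention, or AE-driven switch from 5 mg to placebo. Count each participant once, identify switches from IWRS data, and give the same descriptive comparison with placebo.
2. In SAP 4.11.4.13, show the number and percentage de-escalated by randomized arm and dose step, including blinded de-escalations in the placebo arm. The placebo arm cannot have a 5 mg-to-placebo switch, so its de-escalation count is needed beside the supplementary row to judge background use of the rule.
3. In SAP 4.11.4.13, state that the de-escalation summary is by treatment.

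The cost is small. The IWRS already dispenses de-escalated doses, and SAP 4.11.4.13 already requires de-escalated participants to be identified. The additions amount to one table row, a short count and a few words. The downside is a slightly less favourable supplementary figure beside the existing one. SAP 4.1 would allow such an analysis later without amendment, but specifying it before unblinding avoids choosing it after the result is known.
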